Despite these encouraging results, poor children who participate in ROR still demonstrate language scores that are 6 to 15 points lower than national averages.¹⁷ This may be the result of delays in initiating parent-child verbal interactions until a child's 6-month well child visit. There may be reason to suspect that children exposed to more rich and intensive parent-child verbal interactions prior to six months of age may achieve greater language functioning and outcomes later on.^{19,20} For this reason, we are proposing a study to test the effects of early literacy promotion beginning by 1 month of age with standard child literacy promotion using the ROR model beginning by 6 months of age.

Adverse childhood experiences (childhood adversity) have been shown to have significant impact on the life course of individuals including mental health, chronic disease, and even early death.²¹⁻²⁵ Examples of adversity include abuse, neglect, family dysfunction, and violence, among others. Exposure to adverse childhood experiences (ACE's) is frequent and significant in disadvantaged, minority communities.²⁶ Exposure to chronic stress from adversity leads to altered neurological development and cognitive impairment.²⁷⁻²⁸ For many, adversity is chronic and continues into adulthood. A biological marker of stress is the level of cortisol. Through the measurement of cortisol levels, maternal stress has been shown to negatively impact infant cognitive development and infant-parent attachment.²⁹⁻³⁰ For parents who have chronic exposure to stress and adversity, this likely can negatively impact their interactions with their children and through this mechanism also affect the development of their children.

Understanding how parents' exposure to ACE's influence reading behavior can inform the development of future early childhood development interventions that target communities with high exposure to adversity such as poor communities. Furthermore, understanding contextual factors that influence reading behaviors among parents can serve as additional areas to address in future literacy promotion interventions.

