3.1.1 Screening Phase

Children who attend these clinics are primarily poor (72% Medicaid) and diverse racially with 80% being African-American, 10% white, 5% Hispanic, and 5% Asian. Children will be eligible to participate in this study if they were born ≥ 35 weeks estimated gestational age, without neurodevelopmental disabilities or congenital malformations, with Medicaid insurance (proxy measure for poverty), and < 30 days old at the time of enrollment. Children who are born premature < 35 weeks EGA, who have neurodevelopmental disabilities, or who have congenital malformations are at increased risk of language delays and will be excluded. In addition, we will exclude families who do not speak English or Spanish, as the main measures of reading activity (StimQ, Appendix 6) and language development (Preschool Language Scale-V, Appendix 7) are only available in English and Spanish.

Potential subjects will be identified at the time of their first well child visit < 30 days of life using the electronic health record (EHR). Eligible newborns' parents will be approached at the time of their child's appointment by research staff. They will obtain written informed consent from participants in private. Participants will be randomized to receive either the early literacy promotion arm or the standard literacy promotion arm based on random assignment.

Randomization sequences will be developed by the project biostatistician using computer-generated random numbers prior to study enrollment and will be placed in sealed opaque envelopes. Randomization will ensure equivalence between groups on measured and unmeasured characteristics and is considered to be the strongest protection against bias in study design. Written informed consent will be obtained prior to any study related procedures being performed in person. Consent will include a discussion of study rationale, procedures, measures, benefits, risks, and alternatives to participation. After consent, subjects will either be assigned to the literacy promotion arm or the standard literacy promotion arm of the study. Regardless of their assignment, once they have consented to participate, they will complete a demographic questionnaire (Appendix 1), questionnaires about adverse childhood experiences (Appendix 2), and health literacy (Appendix 3) and the Edinburgh Postnatal Depression Scale (EPDS) (Appendix 4) prior to the intervention.

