Children in both study arms will be followed every 6 months until age 2. Parents will complete study measures consisting of demographic characteristics, postpartum depression symptoms, health literacy, and adverse childhood experiences at enrollment, and parents and children will complete measures of reading activity (Stim-Q), and child expressive and receptive language development (Preschool Language Scale-V) at 6, and 24 months of age. At 12, 18, and 24 months, measures of parental stress (PSI-Short Form, Appendix 9), parental depression (PHQ-9, Appendix 10) will be collected. Child social and emotional competencies will be collected at 18

and 24 months of age (ITSEA, Appendix 11). Information on reading activities and expressive and receptive language outcomes will be collected in concert with scheduled well child visits. Differences in reading activities, parental mental health, child's social/emotional competencies, and language outcomes will be assessed between groups using intention-to-treat analysis. The EHR will be reviewed for children in both arms to count the number of well child visits and examine their vaccination history.

Parents of children who are participating in the study will be informed of the results of their PLS testing in writing. Those whose children score less than 1.5 standard deviations below the mean will be informed that their children's language development is within the average range. Parents whose children who score 1.5 standard deviations or greater below the mean will be informed that their child is exhibiting delays in language development and will be referred for additional evaluations and/or services. In addition, the child's clinician will be informed of their result.

Responses to the question on the PHQ-9 will be checked to determine whether the caregiver has endorsed suicidal ideation. If they have endorsed any of the suicide questions, research staff will administer additional follow up questions and call the study licensed psychiatrist to determine course of action (see Appendix 13-Suicide Protocol). This procedure has been implemented successfully in other studies of parental depression. During the study visits, if a participant was to endorse suicidal ideations, the Appendix 13: 'Suicide Protocol' will be followed to maximize the safety of the participant. At any time, caregivers who endorse suicidal ideations will require immediate follow up with the licensed psychiatrist on call.

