The primary endpoint will be differences in PLS scores at 6 and 24 months of age.

b. Secondary Endpoints

Secondary endpoints will be the difference in StimQ scores at 6, 12, 18, and 24 months of age and the ITSEA scores at 18 and 24 months of age.

c. Statistical Methods

Summary statistics will be obtained, and differences between intervention and control groups will be assessed using intention-to-treat analysis. Cross-sectional differences in StimQ scores and PLS scores between intervention and control groups at the 6 and 24 month study visits and differences in ITSEA scores at 18 and 24 month study visits will be assessed using t-tests. To determine whether early literacy promotion is associated with greater language development, we will develop regression models using longitudinal data methods that adjust for correlation in PLS scores over time and for potential confounding by demographic characteristics. To explore whether early literacy promotion is associated with greater child socio-emotional development, we will develop regression models for scores at 18 and 24 months that adjust for potential confounding by demographic characteristics. To explore the impact of early literacy on healthcare utilization, the EHR will be reviewed to identify a subjects number of well visits and their vaccination history.

To determine whether parent adversity, health literacy, parenting stress, and/or depression modify the effects of early literacy promotion on language development, we will develop similar regression models using longitudinal data methods, but we will also fit interaction terms between study group and ACE score (≥ 4), SAHL (high or low), PSI score, and EPDS score (> 9) or PHQ-9 Score (> 4). To determine if parent-child reading activity mediates the association of intervention group assignment and language development, we will use mediation analysis with separate models regressing group assignment on language development, parent-child reading activity on group assignment, and group assignment on language development adjusted for parent-child reading activity.

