Assuming a power of 0.90, an alpha of 0.05, a 20% loss to follow-up over two years, and a clinically significant difference of 4 points or more on the expressive and receptive subscales of the PLS between groups, we estimate that we will need to recruit a total sample size of 120 eligible children (60 in each group) to participate in the study. All analyses will be conducted using Stata Statistical Software, version 13 (College Station, TX).

We will use NVIVO software to assist in data management for the semi-structured interviews. This software facilitates thematic coding, the assessment of inter-rater reliability, and correlation of themes with demographic variables. After detailed review of each transcript, we will develop a coding scheme and dictionary. We will use the constant comparative method in which newly collected data are compared with categories that have emerged from previously collected data. Through an iterative process, we will discuss the emerging themes as a team and revise the interview guide as needed to explore in depth themes arising from the data. If differences in coding arise, two members will discuss the data and negotiate to reach a consensus. If consensus cannot be reached a third member will decide the outcome. Once thematic saturation is reached, findings will be shared with participants at a follow up focus group after interviews have been conducted.

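### The main PLS model adjusts only for unlisted demographics and omits the enrolment ACE, SAHL and EPDS scores, which may give up some precision

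*Combined protocol and SAP*

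**What the plan says.** Section 5) a makes group differences in PLS at 6 and 24 months the primary endpoint. Section 5) c plans two analyses of it. One is an unadjusted t-test at each of the two visits. The other is a set of longitudinal regression models that "adjust for correlation in PLS scores over time and for potential confounding by demographic characteristics". The section does not list the demographic variables, and it does not say which of the two analyses is primary.

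Other baseline information is collected. Section 3.1.2: "Parents will complete study measures consisting of demographic characteristics, postpartum depression symptoms, health literacy, and adverse childhood experiences at enrollment". Section 3.1.1 places these questionnaires before the intervention. In section 5) c the ACE, SAHL and EPDS scores appear only in the Aim 2 models, in categories, as interactions with study group.

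PLS itself is first measured at 6 months (sections 3.1.2 and 3) c), after the early-literacy period, so there is no baseline value of the outcome.

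**The concern.** Without a baseline PLS, any gain in precision for the main comparison must come from other baseline variables that predict PLS. The protocol gives some reason to expect that the enrolment scores do. Section 1.3 states that "maternal stress has been shown to negatively impact infant cognitive development and infant-parent attachment", and says that parental adversity probably affects child development through the parent's interactions with the child. Aim 2 treats adversity, health literacy and depression as important enough to test as modifiers of the language effect. Yet the model for the main effect leaves all three out.

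The stated purpose of adjustment is also a poor fit. Sections 3.1 and 3.1.1 say that randomisation will make the groups equivalent on measured and unmeasured characteristics. Confounding is then not the reason to adjust; prognosis is. With no list and a confounding rationale, the covariate set remains to be chosen later.

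At stake is the width of the confidence interval for the PLS difference, and how firmly the adjusted estimate is fixed in advance.

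**Working it through.** **The plan's own figure.** The sample-size paragraph of section 5) c starts from "Assuming a power of 0.90, an alpha of 0.05, a 20% loss to follow-up over two years". Its target is a 4-point difference on the two PLS subscales, and it arrives at 120 children, 60 per group. It gives no SD, so 120 cannot be reproduced from the stated inputs. The implied SD can be solved for:

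- Evaluable per arm: 60 × 0.8 = 48, so 96 in total.
- Two-sided test assumed (sidedness is not stated): 1.960 + 1.282 = 3.242.
- SD = 4 / (3.242 × √(2/48)) = 4 / (3.242 × 0.2041) ≈ 6.05.
- Check at SD 6: n = 2 × 3.242² × 36 / 16 ≈ 47.3, so 48 per arm; 48 / 0.8 = 60 per arm, 120 in total.

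An SD of about 6 is therefore back-solved, not an input of the plan.

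**Size of the omission.** The model already adjusts for demographics. The relevant quantity is the partial R-squared (R²) of the added scores beyond demographics. The documents do not give it; 5% to 20% is assumed. For k added covariates and N evaluable children, allowing for the degrees of freedom spent, the variance of the group difference at one visit changes by about

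ratio = (1 − R²) × (N − 3) / (N − k − 3), with N = 96.

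For k = 4 (three scores plus gestational age) the second factor is 93/89 = 1.045. For k = 3 it is 93/90 = 1.033.

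| Assumed partial R² | Ratio, k = 4 | Acts like | Ratio, k = 3 | Acts like |
|---|---|---|---|---|
| 5% | 0.95 × 1.045 = 0.993 | 1% more children | 0.982 | 2% more |
| 10% | 0.90 × 1.045 = 0.940 | 6% more | 0.930 | 8% more |
| 20% | 0.80 × 1.045 = 0.836 | 20% more | 0.827 | 21% more |

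The gain in children is 1/ratio − 1. Break-even is R² = k/(N − 3): 4/93 = 4.3% for four covariates and 3/93 = 3.2% for three. If the added variables explained nothing, the variance would rise by about 4.5% or 3.3%.

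Demographics already in the model use degrees of freedom too, but this barely alters the result. With five demographic terms (assumed) and k = 4, the factor is 88/84 = 1.048 instead of 1.045.

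In standard-error terms, for k = 4, the square roots of 0.993, 0.940 and 0.836 are 0.996, 0.970 and 0.914. The standard error falls by about 0.4%, 3% and 9%.

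**Power.** These gains are not translated into power, because that needs the missing SD. As an illustration only, with 48 per arm and a 4-point difference, unadjusted power is about 0.90 at an assumed SD of 6 and 0.50 at an assumed SD of 10. That spread is far larger than any effect of the covariate choice.

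**Timing.** Section 3) a lists randomisation before the collection of baseline information. Section 3.1.1 says that the questionnaires are completed whatever the assignment, before the intervention. The text does not guarantee that the parent answers before the allocation is known. This matters for self-reported scores used as baseline covariates.

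**The case against.** The strongest case against is that this is a preference about precision. The comparison is randomised, the model already adjusts for demographics, and those may carry much of what the three scores would add. The content of the demographic questionnaire (Appendix 1) is not in the supplied text, so this cannot be checked. If the partial R-squared is near 5% or lower, nothing is gained. This stands, and it limits the point to a possible gain of unknown size.

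Several stronger readings are tempting, but the documents do not support them:

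- *The scores go unused, or are the only baseline predictors available.* The Aim 2 models on language use them, and demographics are collected at enrolment and already adjusted for.
- *The protocol treats all of these variables as predictors of language.* Section 1.3 supports stress and adversity. Health literacy and depression are named as possible effect modifiers, not as predictors of PLS.
- *Gestational age is an established predictor here.* Section 3.1.1 cites the risk of language delay for "Children who are born premature < 35 weeks EGA", but those children are excluded. No gradient is given at or above 35 weeks, the only range enrolled.
- *Covariates will be chosen by observed imbalance.* No such procedure is described. The wording merely fails to rule it out.
- *The gain can be read as power above 90%.* That would take the unadjusted test as comparator and an SD that the plan does not state.

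**Conclusion.** The point holds as one about precision and prespecification. The main-effect longitudinal PLS model names only unlisted demographics, gives confounding as the reason, and omits three enrolment scores that the plan already collects and uses elsewhere.

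A reader might infer that the primary comparison is biased or that 120 children is invalidated. Neither follows: under randomisation, leaving out baseline covariates does not bias the comparison or make the test invalid.

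With about 96 evaluable children and four added covariates, the gain runs from roughly nothing at a partial R-squared of 5% to the equivalent of 20% more children at 20%. That range is assumed, and it rests on the planned 20% loss to follow-up and on a comparison at a single visit. The change is worth making because it costs almost nothing, not because the loss is known to be large.

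**What to change.** In section 5) c:

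1. Name the longitudinal model as the primary PLS analysis, and report the unadjusted t-tests at 6 and 24 months as supportive.
2. Replace the confounding rationale with a fixed covariate statement, for example: *The primary PLS model contains arm, visit and arm-by-visit, a short list of demographic variables named here, and enrolment SAHL, EPDS and ACE scores as continuous covariates. The covariates are included as prognostic baseline variables, are fixed in advance, and are kept whatever the observed balance.*
3. Keep the demographics; the scores are added to them and do not replace them. Gestational age in weeks is optional.
4. State how a missing enrolment score is handled, so that no randomised child is lost from the model for that reason.

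In sections 3.1.1 and 3) a, state that the enrolment questionnaires are completed before the allocation is revealed.

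No new data are needed. The statistical cost is three degrees of freedom beyond demographics, or four with gestational age, and a slight loss of precision if the added variables explain less than about 3% to 4% of the remaining variance. The operational cost is the order of steps at the enrolment visit. If any power figure is quoted for the adjusted model, the SD and R-squared behind it should be stated as assumptions.

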2.2 Secondary Objectives

Specific Aim 2: To explore whether Parent history of adversity, health literacy, parenting stress, and depression moderate the effects of early literacy promotion.

Specific Aim 3: To explore whether the effects of early literacy promotion are mediated through the intensity of reading behaviors.

Specific Aim 4: To identify perceptions of barriers to and promoters of reading behavior among parents with high and low ACE scores.

Specific Aim 5: To explore the effects of an early literacy promotion program compared to standard literacy promotion on social-emotional development among poor urban children in Philadelphia.

Specific Aim 6: To explore the impact of early literacy on healthcare utilization

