Children randomized to the standard literacy promotion arm will receive developmentally appropriate books and information on the importance of parent-child reading activity by pediatric clinicians beginning with the 6-month well child visit and weekly text message reminders concerning child safety. This conforms to the ROR National Program recommendations and is considered standard of care at these 3 urban clinics. To prevent contamination in which pediatric clinicians inadvertently provide books and instruction on reading activity to control children prior to 6 months of age, a research assistant will ensure that books and reading instruction are not provided to children in this arm prior to 6 months of age. The weekly text message reminders will be initiated following enrollment, will be standardized according to age, and will be scheduled according to parent preference in the morning, afternoon, or evening.

Children in both study arms will be followed every 6 months until age 2. Information on reading activities, expressive and receptive language outcomes, parental mental health, and child's social and emotional competencies will be collected in concert with scheduled well child visits. Differences in reading activities, parental mental health, child's social/emotional competencies, and language outcomes will be assessed between groups using intention-to-treat analysis.

A purposive sample of up to 30 parents of infant less than 6 months old who have consented to participate in the main study will additionally be recruited to participate in semi-structured interviews with aims to have an equal mixture of parents with high and low exposure to adversity. High adversity is defined for the purpose of this study as having an ACE score of 2 or greater. Low adversity is defined for the purpose of this study as having an ACE score less than 2. Parents with infants less than six months of age are specifically being targeted for the interviews to understand factors that affect this specific age group. The interviews will aim to explore and to understand barriers to reading, parents' perceptions of the value of reading to infants, and factors which promote reading in this population

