 - Parents will complete measures of reading activity (Stim-Q) at each study visit.
 - Children will complete measure of child expressive and receptive language development (Preschool Language Scale-V) at 6- and 24-month visits.
 - At the 12-, 18-, and 24-month visits, parents will complete the PSI and PHQ-9 questionnaires.
 - At the 18- and 24-month visits, parents will also complete the ITSEA about their child.

4) STUDY EVALUATIONS AND MEASUREMENTS

a. Screening and Monitoring Evaluations and Measurements

i. Parent Adversity (ACE)

The 9 ACE questions query adults as to their exposure to 9 different adverse childhood experiences (economic hardship, domestic violence, parent mental health, discrimination, parent substance abuse, divorce, parent death, parent incarceration, and neighborhood violence) and are contained in the 2011-12 National Survey of Children's Health, a nationally representative telephone survey.

ii. Parent Health Literacy (SAHL)

The Short Assessment of Health Literacy (SAHL) is a validated measure of health literacy for English- and Spanish-speaking populations.

iii. Parent Depressive Symptoms (EPDS)

The Edinburgh Postnatal Depression Scale (EPDS) is a validated 10-item scale for postpartum depression symptoms with scores ≥ 9 having a sensitivity of 97% and specificity of 43% for major or minor depression.

iv. Reading Activity (StimQ)

The StimQ is an office measure of cognitive stimulation at home available in Spanish and English, and the Read subscale of the StimQ contains questions on the frequency of parent-child reading activity and the number and variety of books at home.²⁴ Psychometric analysis of the StimQ shows high internal consistency (Cronbach's Alpha=0.89) and test-retest reliability ($r=0.84$) and moderate correlation with the Bayley Scales of Infant Development ($r=0.52$, $p<0.001$).

We will also use a brief reading questionnaire (Appendix 12) about when participants began reading to their child and what influenced that decision.

v. Language Development (PLS)

The Preschool Language Scale-5th Edition (PLS) is a validated measure of expressive and receptive language function among children from birth through 7 years of age and is available in Spanish and English. The PLS has been standardized in over 1400 children nationally with a sensitivity of 0.83 and a specificity of 0.80 for the detection of language delay.

vi. Infant Toddler Social Emotional Assessment (ITSEA)

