The ITSEA assesses for social or emotional problems and competencies in infants and toddlers and was designed to identify children with deficits or delays in these areas. It provides a comprehensive profile of problems and competencies with scores on 4 domains: 1) Externalizing 2) Internalizing 3) Dysregulation 4) Competence. Each domain is comprised of a number of subscales. The ITSEA also yields scores on three clusters that include atypical behaviors: Maladaptive, Social Relatedness, and Atypical.

vii. Patient Health Questionnaire – 9 (PHQ-9)

The Patient Health Questionnaire (PHQ) is a self-administered version of the PRIME-MD diagnostic instrument for common mental disorders. The PHQ-9 is the depression module, which scores each of the 9 DSM-IV criteria as “0” (not at all) to “3” (nearly every day). A PHQ-9 score ≥ 10 had a sensitivity of 88% and a specificity of 88% for major depression.

viii. Parenting Stress Index (PSI)

The PSI Short Form (PSI/SF) is a direct derivative of the Parenting Stress Index (PSI) full-length test. All 36 items on the Short Form are contained on the Long Form with identical wording and are written at a 5th-grade reading level, for parents of children 12 years and younger. The PSI/SF yields a Total Stress score from three scales: Parental Distress, Parent-Child Dysfunctional Interaction, and Difficult Child. Scores at or above the 85th percentile are considered high and Defensive Reponding scores at 10 or below are considered extremely low.

ix. Qualitative Measures

An interview guide with appropriate probes will be utilized to guide the semi-structured interviews. Areas that will be investigated include: understanding parent's perception of value in reading to their infant, factors that promote reading, and barriers that inhibit/limit reading. Elements of parent characteristics, family support and structure, and community factors will be explored through semi-structured interviews. As is typical in qualitative research, the order of questions and phrasing may change iteratively without changing content or risk. A purposive sample of parents as described previously in the section regarding the investigational plan will be selected to participate in the interviews. Interviews will be conducted with the goal to achieve

thematic saturation and elicit themes. The interviews will be recorded, transcribed, and stored on a secure CHOP server.

5) STATISTICAL CONSIDERATIONS

a. Primary Endpoint

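### Aim 2 splits numeric moderator scores at unexplained cut-offs that differ from thresholds given elsewhere; continuous enrolment scores would keep more information

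*Combined protocol and SAP*

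**What the plan says.** Aim 2 is a secondary, exploratory objective (section 2.2): "To explore whether Parent history of adversity, health literacy, parenting stress, and depression moderate the effects of early literacy promotion". Section 5)c carries it out with longitudinal regression models of PLS that contain "interaction terms between study group and ACE score (≥ 4), SAHL (high or low), PSI score, and EPDS score (> 9) or PHQ-9 Score (>", where the list ends with a PHQ-9 cut of 4. PSI is the only moderator listed without a cut-off. No boundary is given for high or low SAHL. The depression term reads "EPDS score (> 9) or PHQ-9 Score (> 4", with no rule for choosing between the two instruments.

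The same instruments appear elsewhere with other thresholds:

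- **ACE.** Section 4)a.i: "The 9 ACE questions query adults as to their exposure to 9 different adverse childhood experiences", so the score runs from 0 to 9. Section 3.1, in the paragraph on the interview sub-study: "High adversity is defined for the purpose of this study as having an ACE score of 2 or greater".
- **EPDS.** Section 4)a.iii: "scores ≥ 9 having a sensitivity of 97% and specificity of 43% for major or minor depression".
- **PHQ-9.** Section 4)a.vii: "A PHQ-9 score ≥ 10 had a sensitivity of 88% and a specificity of 88% for major depression".
- **PSI.** Section 4)a.viii: "Scores at or above the 85th percentile are considered high". Section 5)c does not refer to this threshold.

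ACE, health literacy and EPDS are collected at enrolment. PSI and PHQ-9 are collected at 12, 18 and 24 months (section 3.1.2). The sample size in section 5)c, 120 children with 60 per group, is for a between-group difference of 4 points on the PLS subscales. The documents give no power or sample-size figure for Aim 2, no score distributions, and no expected share of parents above any cut.

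**The concern.** There are two problems. First, the Aim 2 splits match none of the thresholds given for the same scores elsewhere, and no reason is offered. A reader of the moderator results cannot carry over the quoted EPDS and PHQ-9 accuracy, and cannot line up the ACE groups with those of the interview sub-study. Section 9 plans one manuscript on moderation and another on barriers to and promoters of reading, so two papers from one cohort would divide parents by ACE at different points.

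Second, splitting a score discards the differences between parents on the same side of the cut. Interactions are estimated less precisely than main effects, and this trial was sized for a main effect only. A loss of information on the moderator is therefore hard to afford, and a real difference in ELP benefit by adversity or depressive symptoms could be missed.

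**Working it through.** **1. Cut-offs side by side (integer scores).**

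| Score | Aim 2 split, 5)c | Threshold elsewhere | What that threshold is | Scores grouped differently |
|---|---|---|---|---|
| ACE | ≥ 4 | ≥ 2 (3.1) | study definition, interview sub-study | 2 and 3 |
| EPDS | > 9, i.e. ≥ 10 | ≥ 9 (4)a.iii) | point at which accuracy is quoted | 9 only |
| PHQ-9 | > 4, i.e. ≥ 5 | ≥ 10 (4)a.vii) | point at which accuracy is quoted | 5 to 9 |
| SAHL | high or low | none | – | cannot be determined |
| PSI | none stated | 85th percentile (4)a.viii) | description of a high score | – |

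**2. What the sample was sized for.** Inputs from 5)c: power 0.90, alpha 0.05, 20% loss, difference 4, 60 per group. Evaluable: 60 × 0.8 = 48 per arm, 96 in all. No SD is given, so the 120 cannot be reproduced. Back-solving for a two-sided test gives SD = 4 × √(48/2) / (1.960 + 1.282) = 6.05. No interaction enters this calculation.

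**3. Precision of an interaction with a split moderator.** Let p be the share of parents above the cut, with equal arms and n children. The variance of the main effect is 4σ²/n. The variance of the difference between the two subgroup effects is 4σ²/(np) + 4σ²/(n(1−p)) = 4σ²/[np(1−p)]. The ratio of standard errors is 1/√[p(1−p)]. With n = 96 and p assumed:

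| p | SE ratio | Parents above the cut (96p) | Per arm |
|---|---|---|---|
| 0.50 | 2.00 | 48.0 | 24.0 |
| 0.30 | 2.18 | 28.8 | 14.4 |
| 0.20 | 2.50 | 19.2 | 9.6 |
| 0.10 | 3.33 | 9.6 | 4.8 |

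The 96 is a planning figure for 24-month completers. The longitudinal model can also use children who have only the 6-month PLS.

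**4. Information kept by the split, normal score.** For a normal moderator and a truly linear interaction, the efficiency of the split relative to the continuous score is φ(z)²/[p(1−p)], where z is the standard normal point with share p above it.

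| p | φ(z) | Efficiency | Loss |
|---|---|---|---|
| 0.50 | 0.3989 | 0.1592/0.25 = 0.637 | 36.3% |
| 0.30 | 0.3477 | 0.1209/0.21 = 0.576 | 42.4% |
| 0.20 | 0.2800 | 0.0784/0.16 = 0.490 | 51.0% |
| 0.10 | 0.1755 | 0.0308/0.09 = 0.342 | 65.8% |

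**5. The same check for skewed counts.** Here efficiency is the squared correlation between the score and its above-cut indicator, under assumed Poisson and negative binomial distributions truncated to the scale.

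- ACE ≥ 4, means 1 to 3: loss from 28.5% (negative binomial, mean 3, 30.2% at or above the cut) to 79.8% (Poisson, mean 1, 1.9% at or above the cut).
- EPDS ≥ 10, means 3 to 7: about 30-68%.
- PHQ-9 ≥ 5, means 3 to 7: about 35-49%.

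**The case against.** The strongest reply is that section 5)c is the only place that specifies the Aim 2 terms. Its ACE, EPDS and PHQ-9 cut-offs are fixed in advance, can be applied as written, and limit the choice of thresholds after the data are seen. Aim 2 is exploratory, and a linear interaction is an assumption too. All of this stands for those three scores. It does not cover SAHL, which has no boundary, or the open choice between EPDS and PHQ-9.

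Four stronger readings are tempting and are not supported:

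- **That the plan contradicts its own definitions of depression.** Sections 4)a.iii and 4)a.vii report accuracy at one threshold each. They define no case and no moderator group, and 5)c attaches no label to its groups. What remains is that the quoted accuracy does not apply to the groups analysed.
- **That Aims 2 and 4 give the same parents opposite labels.** The ACE definition of ≥ 2 serves to balance up to 30 interviewees, and 5)c does not call a score of 4 or more high adversity. The definition is nonetheless worded for the study as a whole, so the difference needs a sentence.
- **That the low EPDS specificity shows the Aim 2 split dilutes any interaction.** The 97% and 43% belong to ≥ 9. The split is > 9, for which no accuracy is given, and raising a cut-off cannot lower specificity. Nor would moving to ≥ 9 be a remedy, since that is the threshold with 43% specificity.
- **That PSI sets a precedent for continuous scores.** The missing cut-off suggests this but does not settle it. The case for continuous terms rests on efficiency.

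**Conclusion.** The point holds as a matter of efficiency and clarity in a secondary analysis. ACE, SAHL, EPDS and PHQ-9 are dichotomised in a trial sized only for a main effect. The ACE split departs without explanation from the one explicit study definition of high adversity. The EPDS and PHQ-9 splits depart from the thresholds whose accuracy is quoted.

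The loss of about 36-66% is conditional on a roughly normal score, a linear interaction and 10-50% of parents above the cut. None of these is in the documents. For a skewed ACE count the loss could be lower or higher, about 29-80% under the distributions assumed here. A reader might take either range as a property of this trial or apply it to every moderator. Neither is warranted: the score distributions are unknown, and PSI has no stated cut. The primary comparison and the sample size of 120 are unaffected. The change should be made but is not critical.

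**What to change.** In section 5)c, enter the enrolment scores ACE (0-9), EPDS and SAHL as continuous terms in the interaction with study arm. Check linearity by adding a quadratic term, and report the estimated ELP effect with its confidence interval at score values stated in advance. Section 4)a.ii does not describe SAHL scoring, so the revised text should say which numeric score is used.

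If categories are kept for display, reconcile the ACE cut-off between Aims 2 and 4 or state why they differ, and give a reason for the EPDS and PHQ-9 cut-offs.

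The cost is wording. The three enrolment measures are already collected, so no new data or visits are needed. The one small downside is that a linear interaction is assumed, which the quadratic term checks.
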